In terms of signals for potential efficacy, there was a numerical, non-significant improvement in the oxygenation index at days 1, 2 and 3 in the MSC treated group compared to the placebo patients. On day 1, the median oxygenation index numerically improved in the MSC versus placebo group from the baseline (2.7 versus 1.1, $p=0.32$). On day 2, the median oxygenation index numerically improved in the MSC versus the placebo group (4.0 versus 2.6, $p=0.29$) and on day 3, the median oxygenation index numerically improved in the MSC versus placebo group (3.0 versus 1.9, $p=0.29$). However, this phase 2a trial of 60 patients with 2:1 MSC to placebo randomization was not powered for any efficacy endpoints, whereas this new Phase 2b trial for ARDS from medical and traumatic causes of ARDS outlined in this clinical protocol will enroll 120 patients and is powered to test for efficacy for respiratory endpoints with 1:1 randomization. In addition, further *post hoc* analysis of the earlier phase 2a trial showed that there was variability in the viability of the MSCs administered from 36 to 85%. This data was available to the investigators only after the trial was completed. By tertiles, the viability was 36-56% ($n=14$), 57-69% ($n=13$), and 71-85%, ($n=13$). Because of this wide range of MSC viability, we carried out a *post hoc* analysis to determine whether there were any significant differences in the levels of the biologic markers in the plasma according to the MSC

viability. There were no differences in the levels of IL-6, IL-8 or RAGE at baseline. However, after adjustment for baseline differences, angiopoietin-2, a marker of vascular leak associated with more severe lung injury in ARDS, was significantly and progressively lower in the intermediate and the highest tertiles of MSC viability. Thus, there appeared to be a viability-dependent effect on plasma angiopoietin-2 levels based on the MSC viability. In addition, analysis of the change in oxygenation index from baseline over two days was carried out in these cell viability subgroups. This analysis showed a non-significant trend for improved oxygenation index in the intermediate and highest tertile MSC viability groups on day 2. The results of this trial have been published recently in *Lancet Resp Med.* (118)

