8.5.1.6 Viability

Viability testing (AO/PI) will be performed on a sample drawn from the final product. A pre-freeze viability of $\geq 70\%$ will serve as a lot release criterion. Viability by AO/PI will be used to freeze cells in a viable dosing strategy.

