Appendix E: Study Product Preparation Protocol

[figure not shown]
SOP/ Step #	STAT: A Phase 2b, Randomized, Double-blind, Placebo-controlled, Multi-center Clinical Trial of Allogeneic Bone Marrow-Derived Human Mesenchymal Stromal Cells for the Treatment of Acute Respiratory Distress Syndrome	Tech Initials /Date
Section C: Confirmation of Subject Stability on the Day of Infusion		
C.1	Patient has met the clinical stability criteria, confirmation to thaw cells received VIA fax: ARDS MSC STUDY ORDERS: Confirmation of subject stability (Start thaw of cells within 15 minutes of receipt of this order). Time notification received: _____	
Section D: Thaw and Reconstitution of Product		
D.1	
If PLACEBO proceed to Step D.7
 
THAW PROCEDURE: Remove the hMSCs from inventory and thaw up to 2 bags at a time if needed. Refer to SOP-0906 "Cellular Therapy Thawing Procedure"
 
  Inspect the bags using FORMS-0120 "Frozen Bag Inspection Prior to Release"  Remove bag(s) from cassette and place into zip lock bag.  If the product bag has leaks or cracks, do not use it and replace with new bag.  Immerse the sealed zip bag containing the frozen hMSCs in the water bath, gently rocking the bag to mix the suspension during the thawing. 	 N/A PLACEBO
D.2	
DOCUMENT:
 
Water Bath Temp: _____ (37°C +/- 3°C)
 
Thaw Start Time (first bag): _____ (Start timer for 30min. Perform viability between 30 min to 1 hours post start of thaw)
 
Thaw Finish Time (last bag): _____
 
Thaw Product Expiration Date/Time: _____ (4 hours post thaw start time first bag)
	
Documented by/Date: _____
 
Checked by/Date: _____
 
 N/A PLACEBO

SOP/ Step #	STAT: A Phase 2b, Randomized, Double-blind, Placebo-controlled, Multi-center Clinical Trial of Allogeneic Bone Marrow-Derived Human Mesenchymal Stromal Cells for the Treatment of Acute Respiratory Distress Syndrome	Tech Initials /Date

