Appendix E: Study Product Preparation Protocol

SOP/ Step #	STAT: A Phase 2b, Randomized, Double-blind, Placebo-controlled, Multi-center Clinical Trial of Allogeneic Bone Marrow-Derived Human Mesenchymal Stromal Cells for the Treatment of Acute Respiratory Distress Syndrome	Tech Initials												
G.5	UCSF Parnassus Heights Patients ONLY: Deliver cells to bedside nurse or doctor.	 N/A												
G.6	Document product issue using FORMS-0124 "Issue Log". Time Released to Courier: _____  N/A if transported by BMT Lab													
DO NOT TAKE THIS PSS TO ICU														
Section H: Quality Control (QC) Testing														
H.1	Use QC sample (from step D.7 or D.8) to inoculate sterility cultures.  Use technique described in SOP-0912 "Sterility Testing for Cellular Therapy Products and management of Positive Cultures".  Label bottles with: DIN, Date, hMSC Clinical Trial and Tech's initials. Aerobic & Anaerobic sterility testing Sent on: _____ by: _____													
H.2	Sterility Results:  Positive Notified to: _____ Date/Time: _____  Negative	Sterility Result review by/date: _____												
H.3	Using QC sample (from step D.8) perform:  WBC count via hemocytometer  Trypan Blue Viability Testing: Refer to SOP-0935 "Trypan Blue Viability Procedure"  Time Viability was Done: _____  Calculations using memacytometer: 
  
 	Viable Cell Count	Total Cell Count (Viable + Non-Viable)	
   
 Side 1			
 
 Side 2			
 
 TOTAL COUNT	(H)	(I)	
  
 $\frac{(\text{H})}{(\text{I})} \div \frac{(\text{I})}{(\text{I})} \times 100 = \frac{(\text{H})}{(\text{I})} \% \text{ Cell Viability (J)}$ 
If % Cell Viability is <70 notify [contact] and [contact] within 24 hours.
		Viable Cell Count	Total Cell Count (Viable + Non-Viable)	Side 1			Side 2			TOTAL COUNT	(H)	(I)	Calculated by/Date: _____ Verified by/Date: _____
		Viable Cell Count	Total Cell Count (Viable + Non-Viable)											

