Appendix E: Study Product Preparation Protocol

SOP/ Step #	STAT: A Phase 2b, Randomized, Double-blind, Placebo-controlled, Multi-center Clinical Trial of Allogeneic Bone Marrow-Derived Human Mesenchymal Stromal Cells for the Treatment of Acute Respiratory Distress Syndrome	Tech Initials																																
H.4	
Calculate TNC count and recovery %:
 
  
 TABLE 4	
 
 QC SAMPLE: Total Cell Count Thawed/Recovered	
 
 Patient Name:	Study ID:	DIN:	Product Code(s)	
   
 Total Cell Count (Viable + Non-Viable)	(I)	
 
 Total Cells/mL = $(10^6) = (I) \div (\# \text{ of large squares counted}) * 2$ (TB Dilution factor) * (any other dilution) * 1×10^4	(K)	
 
 Total Cells thawed/recovered = $(x 10^8) = (K) * 300 \text{ mL}$	(L)	
 
 Total Viable Cells = $(10^8) = (L) * (J)$	(M)	
 
 Viable Cells Recovery (%) = $(M) / (A) \times 100$		
  
 
If % Viable Cells Recovery is <70 notify [contact] and [contact] within 24 hours.
	TABLE 4				QC SAMPLE: Total Cell Count Thawed/Recovered				Patient Name:	Study ID:	DIN:	Product Code(s)	Total Cell Count (Viable + Non-Viable)			(I)	Total Cells/mL = $(10^6) = (I) \div (\# \text{ of large squares counted}) * 2$ (TB Dilution factor) * (any other dilution) * 1×10^4			(K)	Total Cells thawed/recovered = $(x 10^8) = (K) * 300 \text{ mL}$			(L)	Total Viable Cells = $(10^8) = (L) * (J)$			(M)	Viable Cells Recovery (%) = $(M) / (A) \times 100$				
Calculated by/Date: Calculated by/Date:
 
Verified by/Date: Verified by/Date:
 
 N/A PLACEBO  N/A PLACEBO

TABLE 4																																		
QC SAMPLE: Total Cell Count Thawed/Recovered																																		
Patient Name:	Study ID:	DIN:	Product Code(s)																															
Total Cell Count (Viable + Non-Viable)			(I)																															
Total Cells/mL = $(10^6) = (I) \div (\# \text{ of large squares counted}) * 2$ (TB Dilution factor) * (any other dilution) * 1×10^4			(K)																															

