7.2.3 Primary and Secondary Endpoints Adjusted for SARS-CoV-2 Infection

In addition, to better understand the hMSC effects in patients with COVID-19 disease, we will conduct the following analyses:

- The primary and secondary endpoints as stratified in separate analyses by the following binary variables of interest prior to randomization: SARS-CoV-2 Infection status, viral antigen level (greater or less than median value), dexamethasone (or equivalent steroid therapy) and other immunomodulatory agents.
- WHO Scale for Clinical Improvement outcome at baseline, day 7, day 14, and day 28 adjusted by COVID-19 status.
- Gene expression profiles compared by treatment arm and adjusted for or stratified by SARS-CoV-2 Infection, dexamethasone (or equivalent steroid therapy) and other immunomodulatory agents.
- Changes in levels of protein biomarker measurements by treatment arm and adjusted for or stratified by SARS-CoV-2 infection, dexamethasone (or equivalent steroid therapy), and other immunomodulatory agents.
- Analysis of primary and secondary endpoints by latent class analysis (LCA) subphenotype and adjusted for or stratified by SARS-CoV-2 Infection.
- Analyses of primary and secondary endpoints adjusted for or stratified by anticoagulation and antiplatelet treatments.
- Analyses to be adjusted for measures of MSC viability.

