12.8 Adjustments for Stratification and SARS-CoV-2 Infection

Analyses of the outcomes will be adjusted for stratification variables (PaO₂/FiO₂ ratio [<150 mmHg or ≥ 150 mmHg] and trauma vs. non-trauma), APACHE III scores at baseline, and baseline measure, where P-value < 0.20 between treatment group.

To better understand the hMSC effects in patient with COVID-19 disease, the primary and secondary endpoints specified in Section 12.6 and 12.7 will also be summarized and conducted in separate linear mixed-effects regression models, in a fashion parallel to the analyses of the above main primary endpoint models, stratified or adjusted by the following binary variables of interest prior to randomization:

- SARS-CoV-2 infection status obtained from medical chart: yes or no
- COVID-19 as a cause of ARDS which is adjudicated by the study physicians: yes or no
- Viral antigen levels measured by NIH lab (PI: [name]): the value will be categorized by greater or less than median value
- Dexamethasone (or equivalent steroid therapy): yes or no
- Other immunomodulatory agents: yes or no
- Anticoagulation and antiplatelet treatments: yes or no
- MSC viability at the time of administration

Furthermore, the primary and secondary endpoints will be analyzed by latent class analysis (LCA) subphenotype using the same procedures described in previous studies (23-26) and adjusted for SARS-CoV-2 infection. In addition, we will test for an interaction between MSC therapy and the subphenotypes for the clinical outcomes.

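### Two supplementary SAP analyses cannot work as written: SAP 12.8 adjusts arm comparisons for hMSC-only, post-randomization viability, and SAP 12.7.10 uses a mini-BAL change with no baseline sample; the primary model is unaffected

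*SAP*

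**What the plan says.** **Viability.** SAP 12.8 repeats the primary and secondary endpoint analyses in models parallel to the primary one, "stratified or adjusted by the following binary variables of interest prior to randomization". Seven variables follow. Five are coded yes or no, and viral antigen is split at its median. The last is "MSC viability at the time of administration", with no coding, no cut-off and no rule for placebo. SAP 7.2.3 and Protocol 6.2.3 keep viability outside their binary list, in a bullet of its own: "Analyses to be adjusted for measures of MSC viability". That bullet names no measure and no arm.

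The protocol describes three related quantities, all for cells only:
- Pre-freeze AO/PI viability, which already enters the dose: "Viability by AO/PI will be used to freeze cells in a viable dosing strategy" (Protocol 8.5.1.6).
- Post-thaw viability on the infusion day: "Trypan Blue Viability Testing: Refer to SOP-0935" (Appendix E, step H.3), timed by step D.2 as "Perform viability between 30 min to 1 hours post start of thaw".
- Viable-cell recovery, with its own alert: "If % Viable Cells Recovery is <70 notify" (Appendix E, step H.4).

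**Mini-BAL.** SAP 12.7.10 compares protein biomarkers measured in mini-BAL as a change to day 2 from baseline. The comparison is by arm, stratified, and then made in three linear mixed models that adjust for SARS-CoV-2 infection, steroids and other immunomodulators. Protocol 9.8 and SAP 5 schedule one mini-BAL, 48 hours (plus or minus 4) after the start of infusion. Protocol 9.3 gives blood and urine as the pre-infusion biomarker samples. The endpoint in Protocol 6.2.1 and SAP 7.2.1 is the day-2 level.

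**The concern.** A variable used to stratify or adjust a randomized comparison should exist in both arms and be fixed before allocation. Viability at administration meets neither condition, and it is not binary. The mini-BAL analysis needs a sample that nobody plans to take.

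Both questions will be asked of this trial. Protocol 3.6 reports that in phase 2a "there was variability in the viability of the MSCs administered from 36 to 85" per cent, with a post hoc association between viability and angiopoietin-2. Protocol 3.7.2.6 gives sampling of the airspaces, where the cells are proposed to act, as the reason for the mini-BAL. If the text stays as it is, the analyst must settle the placebo coding, the viability cut-off and the outcome of the adjusted mini-BAL models during analysis, with no rule to follow.

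**Working it through.** The plan gives no figure of its own for either analysis, so the check is whether each can be estimated.

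**1. Order of events (Appendix E).** Randomization is step B.3. Thaw begins at D.1 and the viability test follows the start of thaw. Placebo skips the thaw steps, and H.3 is marked not applicable for placebo. The variable is therefore post-randomization and hMSC-only.

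**2. Stratified version.** Any high and low viability strata divide the 60 hMSC patients only. Each stratum holds 0 placebo patients, so there is no arm comparison within it.

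**3. Adjusted version, placebo value unavailable.** SAP 11 includes subjects only in analyses for which they have data, and SAP 9 imputes nothing unless the SAP says so. With columns for intercept, treatment and viability, 60 hMSC and 0 placebo patients remain. Treatment equals 1 for all of them, so the design has rank 2 of 3 and there is no treatment estimate.

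**4. Adjusted version, placebo kept in by some coding.** The reference is the unadjusted comparison, with variance proportional to 1/60 + 1/60 = 2/60.

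- *Median split, placebo as reference.* The treatment coefficient is low-viability hMSC (30 patients) minus placebo (60). SE factor = √[(1/30 + 1/60) / (2/60)] = √1.5 = 1.22.
- *Percentage, placebo 0, uncentred.* The coefficient is the effect extrapolated to 0% viability. SE factor = √[1 + m²/(2s²)], where m and s are the hMSC mean and SD.
  - The phase 2a tertiles in Protocol 3.6 are 36–56% (n=14), 57–69% (n=13) and 71–85% (n=13).
  - Assuming a uniform spread within each, m = (14×46 + 13×63 + 13×78)/40 = 61.9 and s = 13.9.
  - The factor is √[1 + 61.9²/(2×13.9²)] = 3.30.
  - For assumed means of 62 to 80% and SDs of 8 to 14 points, it runs from about 3.3 to 7.1.
- *Percentage centred in the hMSC arm, placebo 0.* The coefficient is the effect at mean viability, with SE factor 1.00.

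**5. What the coefficient estimates.** The simulation used one value per patient, a true arm effect of −1.29 OI points acting in proportion to viability (an assumption), and SD 3 (1.29/0.43):

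| Model | Mean estimate | SE |
|---|---|---|
| Unadjusted | −1.29 | 0.55 |
| Median split, placebo reference | −1.08 | 0.68 |
| Uncentred percentage, placebo 0 | −0.07 | 1.87 |

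The trial and the true effect are the same in each row. Only the coding differs.

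**6. Mini-BAL.** One sample is scheduled per patient and none at baseline, so 0 of 120 change scores can be computed. The three adjusted models therefore have no outcome. A plasma baseline cannot stand in, because SAP 12.7.10 specifies the fluid. The matching bullet in Protocol 6.2.3 speaks of biomarker change without naming mini-BAL, so the mismatch enters with SAP 12.7.10.

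**The case against.** **Both analyses are supplementary.** SAP 12.5 treats the secondary endpoints as exploratory support. This stands. A reader might infer that the primary result is at risk, but the model in SAP 12.6 contains neither viability nor mini-BAL.

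**Not applicable is not the same as missing.** SAP 6.2 gives the two different CRF entries, so the SAP does not strictly order placebo patients to be dropped. This stands, and it makes step 3 conditional. It does not help the stratified version, and it leaves the coding for the adjusted version unstated.

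**The large standard-error factor belongs to a coding that the SAP never states.** This also stands. A reader might infer from 3.3 that the planned analysis loses most of its power. The documents do not support that: the coding nearest to the SAP's description is a median split, with a factor of about 1.22. The phase 2a spread is also a doubtful guide, because Protocol 3.4 says the wash step reduced viability and was dropped for this trial.

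**The measure is less ambiguous than three candidates suggest.** The words in SAP 12.8 exclude pre-freeze viability and point to the post-thaw test; step H.4 measures recovery. This stands for SAP 12.8, but not for the bullets in SAP 7.2.3 and Protocol 6.2.3.

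**Mini-BAL can still be analysed.** SAP 12.5 provides a t-test or Wilcoxon test for continuous variables and allows log-scale biomarker summaries. The first bullet of SAP 7.2.3 promises stratified analyses of the secondary endpoints. A reader might infer that the SAP has no usable mini-BAL method; it has one for the day-2 level. What fails is the change score and the three models built on it.

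**Conclusion.** Both errors hold. They are stated analyses that cannot be carried out as specified, so more than missing detail is at issue. Three viability conclusions need no distributional assumption: the variable is post-randomization, it exists in one arm only, and viability strata have no controls. The loss of all 60 placebo patients depends on treating not-applicable as unavailable. The factor of 1.22 assumes an even split of 60 hMSC patients; the factor of 3.3 assumes phase 2a viability and is an illustration only. The main point is that an unstated coding decides what the treatment coefficient means. For mini-BAL, 0 of 120 change scores can be formed, and the wording conflicts with the day-2 endpoint defined elsewhere in both documents. The consequence is limited to supplementary results. The text should be corrected before unblinding.

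**What to change.** 1. **Viability.** Remove it from the list in SAP 12.8. Amend the viability bullets in SAP 7.2.3 and Protocol 6.2.3 to an exploratory, non-randomized analysis within the hMSC arm. Use the post-thaw percentage as a continuous variable, adjusted for baseline OI and the two stratification variables. Any comparison of viability groups with placebo should be labelled descriptive, with cut-offs stated in advance.

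2. **Mini-BAL.** In SAP 12.7.10, delete the reference to baseline for mini-BAL. Compare day-2 (log) values between arms in a linear model with the stratification variables and, in turn, SARS-CoV-2, steroid and immunomodulator status. A patient random effect cannot be separated from residual error with one value each. Report by arm how many patients were not sampled and why (death, extubation, Appendix G exclusion). Keep change-from-baseline models for plasma, which has a pre-infusion sample.

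3. **Clerical reconciliations only.** Add 30 h to the ventilator-parameter footnote in Protocol Appendix A and SAP Table 2. Align the ventilatory-ratio times in SAP 12.7.1 with SAP 7.2.1 (30 h and days 2, 3 and 7). Reconcile day-3 gene expression with Paxgene collection, which Protocol 9.8 schedules only before infusion and on day 2.

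The cost is SAP and protocol wording. No patient, sample or procedure is added: post-thaw viability is already tested for hMSC products, and the CRF already requires reasons for missing data.

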12.9 Interim Analyses

One interim analyses will be performed on primary and secondary endpoints, as well as safety endpoints after the enrollment of the 60 patients. Final analysis will occur on 120 patients at the end of the study, after all study close-out activities are completed and the data are locked.

13 SENSITIVITY ANALYSES

13.1 Primary Efficacy Endpoint: Oxygenation Index

Per our previous experience in the recent Phase 2a trial, it is common that oxygenation index will be missing over time, because either the patient has expired due to worsening medical condition, or the ventilator settings have been modified to pressure support mode due to improvement in the patient's medical condition (in this mode, mean airway pressure cannot be measured reliably), or the patient is extubated. Therefore, we will run a sensitivity analysis for oxygenation index using the same methodologies in **Section 12.3**, in the subgroup who will still be on an assisted mode of ventilation at 36 hours.

13.2 Analysis of Per Protocol Population

The primary and secondary efficacy endpoints will be analyses using Per Protocol Population as the sensitivity analysis after the study data is locked upon the completion of study close-out activities.

14 QC PLANS

Original Statistical Data Analyst performs a visual inspection of the code and output to confirm functionality.

